Is the perfusion index an accurate predictor of return of spontaneous circulation in cardiac arrest?

NCT: pending

STUDY SUMMARY

Title

Is the perfusion index an accurate predictor of return of spontaneous circulation in cardiac arrest?

Methodology

A perspective observational double blind study

Outcomes

Return of spontaneous circulation in a mixed population of out-of-hospital and in-hospital cardiac arrest

Study Duration

Estimated duration for the main protocol (e.g. from start of screening to last subject processed and finishing the study) is approximately 2.5 years

Study Center

Monocentric: Centre Hospitalier Universitaire Saint Pierre, Brussels, Belgium

Objectives

Primary Objective: To evaluate the sensibility and specificity of the perfusion index in predicting further return to spontaneous circulation

Secondary Objectives: To compare perfusion index specificity and sensibility in predicting further return to spontaneous circulation compared to end-tidal CO₂

Number of Subjects

92 non-randomized patients in one arms

Main Inclusion Criteria

Inclusion Criteria

- Male and female patients, 12-99 years old, in any distribution.
- Cardiac arrest with an indication to reanimate
- Consent and compliance with all aspects of the study protocol, methods, providing data during the cardiac arrest management

Exclusion Criteria

- Male and female patients younger than 12 years old or older than 99 years old.
- Prisoners
- Pregnant women

Study parameter

- Perfusion index during cardiac arrest

Statistical

Methodology

Primary Endpoint:

Sensibility and specificity of the perfusion index in predicting a return of spontaneous circulation (ROSC)

Secondary Endpoints:

Comparison of receiver operator curves from the perfusion index and the end-tidal CO₂ in predicting ROSC

Determination of the receiver operating characteristic curve of an index combining perfusion index with ETCO₂ and current rhythm

Tertiary Endpoints:

Sensibility and specificity of the perfusion index in predicting further arrest following an initial ROSC

Purpose:

The primary objective is to evaluate the sensibility and specificity of the perfusion index, measured during chest compressions for cardiac arrest, in predicting ROSC.

Background:

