Cardiac arrest prognostication is important in to inform the decision to cease resuscitation or, in the prehospital setting, to inform the decision on transport to hospital. Currently the only intra-arrest monitoring tools widely available with proven prognostic value are the underlying cardiac rhythm identified on electrocardiogram and end-tidal CO₂ (ETCO₂) measurement. Shockable rhythms, namely ventricular fibrillation and pulseless ventricular tachycardia, are associated with better outcomes than non-shockable rhythms such as pulseless electrical activity and asystole.

ETCO₂, so far, is considered the best tool available for prognostication during in or out-of-hospital cardiac arrest. Previous studies have examined ETCO₂ readings and trends at various times during cardiac arrest as a possible predictor of ROSC, survival to admission, and survival to hospital discharge. Nonetheless, ETCO₂ values have numerous limitations and no value alone can safely and accurately predict the chances of return to a spontaneous circulation (ROSC) or can safely inform on the futility of further reanimation. It would be therefore interesting for the clinician on the ground to be able to rely on a panel of different parameters to assess the chances of ROSC in a multimodal way.

Goals of the study:

1. To examine the association between absolute values of the perfusion index during resuscitation and ROSC.
2. To examine the association between the change in perfusion index values during resuscitation and ROSC.
3. To compare the performance of the perfusion index to ETCO₂ in predicting the chances of ROSC.
4. To study a combined index including rhythm, ETCO₂ and perfusion index achieves in predicting ROSC.
5. To study the ability of perfusion index to predict further arrests in patients further re-arrests in patients that achieved an initial ROSC

Duration of the Study:

The study is estimated to complete enrollment within 12 months from study initiation; however, enrolment will remain open until the study goal is met. The duration of this study for each subject will be a maximum of two years.

Product Description:

Perfusion index will be measured a the finger tip using a Radical 97 monitor (Masimo, Irvine, California). Masimo Signal Extraction Technology (SET[®]) pulse oximetry yields continual and simultaneous absolute values and trends.

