All subjects that will be treated by the mobile intensive care unit of CHU Saint Pierre during study period will be screened for eligibility. Subjects having regained a sufficient neurological awareness to sign an informed consent for the study will review and undergo informed consent.

This study will be listed at www.clinicaltrials.gov.

Data collection and reporting.

Data will be collected throughout the intervention up until death or hospital admission or intensive care admission whichever comes first.

Expected outcomes.

It is the sponsor's expectation that higher perfusion index and upwards trends will be associated with higher chances of ROSC during ALS. Moreover, the sponsor expectation is that lower perfusion index following ROSC will be associated with higher chances of re-arrest. Finally the sponsor expect that a combined index including PI, ETCO₂ and rhythm would overperform each of these items in terms of capacity of predicting ROSC chances.

Adverse reactions.

There is no expectation of any adverse outcomes or reactions due to a patient being monitored with a Radical 97 monitor. Any adverse reactions should be reported immediately to the principal investigator or co-investigators

Reasons for Withdrawal or Termination

A subject may be discontinued from the study at any time if the subject, the Investigator, or the Sponsor feels that it is not in the subject's best interest to continue.

The following is a list of possible reasons for study treatment discontinuation:

- Screening Failure
- Subject withdrawal of consent
- The treating clinician is not compliant with study or ERC procedures
- Adverse Event that in the opinion of the Investigator would be in the best interest of the subject to discontinue study participation
- Protocol violation requiring discontinuation
- Mechanical – technical failure of the monitor

Handling of Participant Withdrawals of Termination:

Although subjects may withdraw from the study at any time and for any reason, (or may be withdrawn according to the abovementioned pre-specified cases), subject withdrawal should be avoided as much as reasonably possible.

Premature Termination or Suspension of Study:

This study may be temporarily suspended or prematurely terminated if there is sufficient reasonable cause. Written notification, documenting the reason for study suspension or termination, will be provided by the suspending or terminating party to the Investigator, and the Sponsor.

SAMPLE SIZE JUSTIFICATION

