Sample Size Calculations

We an expected sensitivity and specificity of 90% for PI to predict ROSC, an expected prevalence of ROSC of 40%, a precision of 10% and a type I error rate of 0.05 we calculated a required sample size of 87. Including a possible dropout of 5% we calculated a final sample size of 92.

STATISTICAL ANALYSIS PLAN

Primary Endpoint

We will determine the predictive value of PI measures for ROSC. We will calculate the sensitivity and specificity at multiple different PI thresholds along with corresponding 95% confidence intervals. Overall discrimination of PI for ROSC will be presented as area under the receiver operator characteristic curve (AUC/ROC). PI values will be averaged on two minutes. Each value will be tested for its ability to predict ROSC during the following ALS cycle (2 minutes). To assess the trending ability of PI to detect ROSC we will measure the difference (ΔPI) between initial PI and PI values of the cycle preceding ROSC or the last cycle in the absence of ROSC. We will then examine the association between ΔPI and ROSC through a multivariable logistic regression while adjusting for predetermined baseline confounders such as age, initial rhythm, noflow time, bystander CPR and sex.

Secondary Endpoints

Superiority analysis of PI compared to ETCO₂ in predicting ROSC. Initial and final values of both PI and ETCO₂ will be assessed for their ability to predict ROSC. Moreover averaged values per 2 min cycle will be assessed for their ability to predict ROSC in the following cycle. The constructed ROC curves will be compared using the algorithm suggested by De Long.

Tertiary Endpoints

As a tertiary endpoint we will study the predictive value of PI to predict further re-arrest following a ROSC. Overall discrimination of PI for re-arrest will be presented as area under the receiver operator characteristic curve (AUC/ROC). PI values will be averaged on two minutes. Each value will be tested for its ability to predict a re-arrest during the following 2 minutes.

ASSESSMENT OF SAFETY

Adverse events (AE) will be monitored and collected by the study team during the monitoring phase of the study. For each AE, a detailed explanation will be obtained from the treating physician and medical record. All AEs will be recorded on the CRFs.

Definition of Adverse Event

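### The change in PI (ΔPI) is given a detection aim, but the only analysis named for it is an adjusted association, which cannot by itself support a statement about ability to detect ROSC

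*Protocol*

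**What the plan says.** The protocol's Study Summary defines the primary endpoint as an accuracy measure: "Sensibility and specificity of the perfusion index in predicting a return of spontaneous circulation (ROSC". The Purpose section repeats this: "The primary objective is to evaluate the sensibility and specificity of the perfusion index, measured during chest compressions for cardiac arrest, in predicting ROSC".

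The Primary Endpoint paragraph of the statistical analysis plan treats two forms of PI differently.

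- **Absolute PI**, averaged over two minutes: "We will calculate the sensitivity and specificity at multiple different PI thresholds along with corresponding 95% confidence intervals", plus an AUC. Each value is tested against ROSC in the next two-minute cycle.
- **ΔPI**, measured from the initial PI to the cycle just before ROSC, or to the final cycle if there is no ROSC. The aim is stated as "To assess the trending ability of PI to detect ROSC we will measure the difference (ΔPI". The analysis is "We will then examine the association between ΔPI and ROSC through a multivariable logistic regression", "adjusting for predetermined baseline confounders such as age, initial rhythm, noflow time, bystander CPR and sex". No ROC curve, AUC, cut-off, sensitivity or specificity is named.

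Elsewhere, change in PI is described only in terms of association. Goal 2 reads "To examine the association between the change in perfusion index values during resuscitation and ROSC", and Expected outcomes states that "higher perfusion index and upwards trends will be associated with higher chances of ROSC during ALS".

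**The concern.** Detection is a matter of classification: how often a rising PI is seen in patients who go on to ROSC, and how often in those who do not. A regression coefficient conditional on age, sex, rhythm, no-flow time and bystander CPR does not measure that. It can be clearly different from zero while the two groups overlap heavily.

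The other PI analyses in the plan have a discrimination measure: per-cycle PI has an AUC, initial and final PI have ROC curves (secondary endpoint), and PI for re-arrest has an AUC (tertiary endpoint). ΔPI is the exception, although its sentence sets a detection aim under an accuracy endpoint.

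The Background says that prognostication informs decisions to cease resuscitation or to transport. The Product Description says that PI is relative to the site and the patient, which makes within-patient change a natural quantity to read at the bedside. If only the regression is run, the study would have nothing on which to base a statement about how well the trend detects ROSC.

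**Working it through.** **1. The plan's own figures.** Inputs from Sample Size Calculations: expected sensitivity and specificity 90%, ROSC 40%, precision 10% (read as half-width), type I error 0.05, dropout 5%.

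- ROSC cases needed: 1.96² × 0.9 × 0.1 / 0.1² = 34.57.
- Patients needed: 34.57 / 0.40 = 86.4, so 87.
- With dropout: 87 / 0.95 = 91.6, so 92.

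Both stated figures reproduce. The check below therefore uses 87 to 92 patients and 40% ROSC; 92 patients give about 37 with ROSC and 55 without.

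**2. Assumptions.** The protocol gives no effect size or distribution for ΔPI. I assume a normal ΔPI and take an odds ratio (OR) of 2 per SD as the main case, with a range in step 5.

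**3. Logistic model.** logit P(ROSC) = a + ln(2)·x, with x standard normal and a set so that average P(ROSC) is 0.40 (a ≈ −0.45).

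- AUC ≈ 0.68.
- Sensitivity at 90% specificity ≈ 27%.
- Unadjusted power at 87 patients, by simulation: about 84%.

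**4. Cross-check with two normal groups of equal variance.** Here the separation in SD units is d = ln(OR) = ln 2 = 0.693.

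- AUC = Φ(d/√2) = Φ(0.490) = 0.69.
- Sensitivity at 90% specificity = Φ(d − 1.282) = Φ(−0.588) = 28%. By symmetry, specificity at 90% sensitivity is the same.
- Standard error of d ≈ √(1/37 + 1/55) = 0.213, so z = 0.693 / 0.213 = 3.26 and p ≈ 0.001.

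So a result at about p = 0.001 corresponds to an AUC near 0.69.

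**5. Range, with adjustment.** Simulated logistic regressions with 92 patients, about 40% ROSC, adjusted for the five named covariates (1,500 per row; covariate effects assumed, because the protocol gives none):

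| True adjusted OR per SD | Share with p < 0.05 | Median AUC of ΔPI when p < 0.05 | Median specificity at 90% sensitivity when p < 0.05 |
|---|---|---|---|
| 1.8 | 68% | 0.67 | 28% |
| 2.0 | 82% | 0.68 | 30% |
| 2.25 | 89% | 0.70 | 33% |
| 2.5 | 95% | 0.71 | 34% |

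Across these rows, 76% to 96% of the significant results had an AUC below 0.75. Over this range, significance says little about whether ΔPI discriminates well.

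**The case against.** The strongest reply is that the regression fits the question asked about change in PI. Goal 2 and Expected outcomes both speak of association, and so does the sentence that names the regression. Adjustment for prespecified baseline confounders is ordinary for that purpose. This stands: the regression is the right answer to Goal 2 and should stay.

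A reader might go further and infer that the plan draws a conclusion about detection that its analysis cannot support. The documents do not bear that out. They state no conclusion, decision rule or significance criterion for ΔPI. The primary endpoint is also not left without an accuracy analysis, because absolute PI has one. A reader might also hold the ΔPI figures against the 90% sensitivity and specificity in the sample size section. That assumption is made for PI predicting ROSC, not for ΔPI, so the comparison is not a fair one.

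It can also be said that a c-statistic or ROC curve for a named model may be left to a separate analysis plan. That has some force, and nothing in the protocol excludes such outputs. But this protocol does fix the discrimination outputs for the other PI analyses, and for ΔPI it pairs a detection aim with an association method. The mismatch is in the text itself.

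A last objection is about the remedy. ΔPI as defined ends at a cycle that can be identified only once the outcome is known, so a ROC curve for that quantity would be retrospective and could be mistaken for real-time accuracy. This is correct, and the fix has to deal with it.

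**Conclusion.** The point holds in a limited form and is minor. One sentence gives ΔPI a detection aim under an endpoint defined by sensitivity and specificity, while the only method named measures adjusted association. That method answers Goal 2 but cannot by itself support a statement about ability to detect ROSC. For an assumed OR of 2 per SD, a significant result is likely (about 82% adjusted with 92 patients, about 84% unadjusted with 87), with an AUC of about 0.68 and sensitivity of about 27% at 90% specificity.

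These figures rest on a normal ΔPI, on chosen effect sizes and, in the adjusted runs, on assumed covariate effects. They show what can happen at this sample size; they do not predict what the study will find.

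**What to change.** Keep the adjusted logistic regression, and label it as the analysis for Goal 2. Add for ΔPI the outputs already planned for absolute PI: ROC curve, AUC, and sensitivity and specificity at stated thresholds with 95% confidence intervals.

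For these outputs, define ΔPI at each two-minute cycle as that cycle's PI minus the initial PI, and test it against ROSC in the following cycle. This matches the scheme for absolute PI and uses only information available at the time. Since a patient contributes several cycles, the confidence intervals should allow for that, for example by resampling patients. Base any statement on trending or detection ability on these outputs.

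The least that would remove the inconsistency is to reword the aim as association, in line with Goal 2; the study would then make no claim on detection by trend.

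The cost is a little more analysis of data already collected, with no change to conduct. The downside for the sponsor is that the trend result may look less favourable than a significant coefficient would suggest.

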Perfusion index (PI) is an assessment of the pulsatile strength at a specific monitoring site, and as such PI is an indirect and noninvasive measure of peripheral perfusion. It is calculated by means of pulse oximetry by expressing the pulsatile signal as a percentage of the nonpulsatile signal, both of which are derived from the amount of infrared (940 nm) light absorbed. The PI value is relative to a particular monitoring site, (e.g. the fingertip or toe), of each patient as physiological conditions vary between monitoring sites and individual patients.

Potential Benefits and Risks to Patients:

No foreseeable benefit can be expected on included patients.

Given the observational design and the well studied effects of continuous non-invasive infrared pulse oximetry monitoring we can reliably declare that we expect no possible harm to the patients included in the study.

Methods:

Study Design.

Double-blind study involving ninety two subjects treated with advanced life support according to the European Resuscitation Council (ERC) recommendations will be included in one observatory arms. Patient treatment during resuscitation will be determined by the treating clinician within the frame of ERC recommendations. Monitoring of perfusion index will be initiated as soon as possible and recorded until the end of the resuscitation efforts. ETCO₂ will be placed as soon as possible and recorded until the end of the resuscitation irrespectively if measured while the patient is ventilated through a bag-valve-mask or through a advanced infraglottic airway.

Study population and selection criteria.

All aspects of the study and consent forms will be approved by our Ethical Board prior to implementation. All patients in cardiac arrest, after application of the inclusion and exclusion criteria, with an indication to initiate an advanced life support will be included in the study. Included participants that will be successfully reanimated and that will regain a sufficient level of consciousness will be required to sign a full informed consent.

Inclusion criteria will be a cardiac arrest in a subject aged between 12 to 99 years old with an indication to start an ALS.

Subjects will be excluded from the study if younger than 12 years old, if pregnant or if prisoners at study inclusion.

We aim to recruit 90 patients in cardiac arrest for whom an ALS has been initiated.

Recruitment methods.

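### The outcome decides where the ΔPI interval ends, so any drift of PI during CPR biases the trend analysis (Goal 2)

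*Protocol*

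**What the plan says.** The Protocol's Statistical Analysis Plan, under Primary Endpoint, sets two kinds of analysis of PI against ROSC.

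- **Level of PI.** Two-minute means are used: "Each value will be tested for its ability to predict ROSC during the following ALS cycle (2 minutes").
- **Trend of PI.** The measure is the "difference (ΔPI) between initial PI and PI values of the cycle preceding ROSC or the last cycle in the absence of ROSC". ROSC is regressed on it in a multivariable logistic model, "adjusting for predetermined baseline confounders such as age, initial rhythm, noflow time, bystander CPR and sex".

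Under Study Design, "Monitoring of perfusion index will be initiated as soon as possible and recorded until the end of the resuscitation efforts". The second item under Goals of the study is "To examine the association between the change in perfusion index values during resuscitation and ROSC", and ΔPI is the only analysis stated for it. Under Expected outcomes the sponsor anticipates that "higher perfusion index and upwards trends will be associated with higher chances of ROSC during ALS".

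**The concern.** In a patient with ROSC the interval closes because ROSC occurred. In a patient without ROSC it closes when efforts stop. ΔPI is a raw difference, not a rate, and there is no common time point at which all patients are compared. The list of adjusters is open-ended, but only to baseline factors, and elapsed CPR time is not one.

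Two conditions together produce bias: PI drifts during CPR, and the intervals differ in length between the groups. Then ΔPI separates the groups even if PI says nothing about ROSC. With a general fall in PI, and ROSC patients observed for less time, those patients show the smaller fall. That looks like the upward-trend association the sponsor expects. With a general rise, a true association can be hidden or turned round. If either condition is absent there is no bias.

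**Working it through.** **1. The plan's own figure.** Under Sample Size Calculations, 1.96² × 0.9 × 0.1 / 0.10² = 34.57 patients with ROSC. Dividing by 0.40 gives 86.4, rounded up to 87, and 87 / 0.95 = 91.6 gives 92. Both stated figures reproduce. They rest on sensitivity and specificity, so ΔPI does not affect them.

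**2. Inputs.** From the Protocol: the ΔPI definition, the five baseline covariates, 92 patients, 40% ROSC and two-minute cycles. Assumed, because the Protocol gives none of them: drift, spread of slopes between patients, chance of ROSC per cycle, and stopping time. Slopes are allowed to vary because Product Description notes that "physiological conditions vary between monitoring sites and individual patients".

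**3. Size of the shift.** Let PI for patient i at cycle j be aᵢ + (d + bᵢ)·j + noise (SD 1), where d is the common drift and bᵢ has mean 0 and is unrelated to outcome. With the interval ending at cycle T,

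mean ΔPI (ROSC) − mean ΔPI (no ROSC) = d × (mean T with ROSC − mean T without).

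- Base case: a 3.65% chance of ROSC per cycle with stopping near cycle 14 (SD 3) gives about 40% ROSC, since 1 − 0.9635¹⁴ ≈ 0.41. Mean T is 6.7 versus 13.7. At d = −0.1 the shift is −0.1 × (6.7 − 13.7) = +0.70 SD.
- Shorter efforts: 5.05% per cycle with stopping near cycle 10 (SD 2.5) gives mean T of 4.9 versus 9.7, and −0.1 × (4.9 − 9.7) = +0.48 SD.
- Falling chance of ROSC: 0.09·exp(−0.15·(cycle − 1)) gives about 44% ROSC and mean T of 4.5 versus 13.9, and −0.1 × (4.5 − 13.9) = +0.94 SD.

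The 6.7 leaves out patients with ROSC in cycle 1, who have no preceding cycle. Keeping them with the initial cycle as end point gives 6.2, and a shift of −0.1 × (6.2 − 13.7) = +0.75 SD.

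**4. False positives when PI is unrelated to ROSC.** Simulation of the planned logistic model (1,500–2,000 studies per case, two-sided 5%), in percent:

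| Case | Drift per cycle | Slope SD 0 | 0.1 | 0.2 |
|---|---|---|---|---|
| Base | 0 | 5.1 | 4.2 | 3.1 |
| Base | −0.02 | 6.8 | 5.0 | 4.5 |
| Base | −0.05 | 20.1 | 11.4 | 7.0 |
| Base | −0.1 | 57.1 | 39.6 | 19.3 |
| Base | +0.1 (opposite direction) | 56.4 | 39.1 | 19.8 |
| Shorter efforts | −0.05 | 11.1 | 9.7 | 6.8 |
| Shorter efforts | −0.1 | 31.8 | 25.3 | 15.8 |
| Equal durations | −0.2 | 6.1 | not run | 5.3 |
| Falling chance of ROSC | −0.1 | 82.2 | 63.5 | not run |
| Falling chance, drift levels off | −0.1 at first | 21.3 | 19.1 | not run |

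With a constant chance of ROSC and a drift that starts at −0.1 and levels off, the rate is about 7–10%.

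**5. A second set of assumptions.** With 87 patients, 35 with ROSC, noise SD 0.5 on ΔPI and no covariates, mean durations of 6 versus 9 cycles give 23% at drift −0.05 and 61% at −0.10 (drift now in PI units). Durations of 5 versus 12 give 84% and 99.9%. Equal durations (7 versus 7) give 4–5% at every drift.

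**6. Masking.** With an assumed true log-odds of 0.4 per SD of change and slope SD 0 (0.1), the planned ΔPI is significant in the right direction in 69.5% (78.3%) of studies without drift and in 4.5% (13.9%) at drift +0.1. At +0.2 it is significant in the wrong direction in 44.6% (10.9%).

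**7. The per-cycle analysis of PI level.** It does not use this interval, but it is not thereby cleared. If cycles are pooled without a term for elapsed cycle and the chance of ROSC falls over time, false positives are 14.9% at drift −0.1, 35.0% at −0.2 and 13.3% at +0.1 (slope SD 0). With a cycle term the rate is 5.7%. With a constant chance of ROSC it is 5–6%.

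**The case against.** - **The drift is not shown.** Nothing in the Protocol says that PI drifts during CPR, in either direction. The larger figures assume a straight-line drift over about 14 cycles (28 minutes), and a drift that levels off shrinks them a good deal. This stands: confidence attaches to the mechanism, not to the size in this study.
- **ΔPI is supportive.** The primary endpoint is sensitivity and specificity, the sample size is built on it, and no test or alpha is set for ΔPI. This also stands and limits the seriousness. It does not remove the problem, because the odds ratio is biased whether or not it is tested. The false-positive rate only expresses that bias on a familiar scale.
- **A simpler repair exists.** Adding elapsed cycles to the planned model gave 3.8–4.7% false positives under the second set of assumptions. At drift −0.1 in the base set-up it gave 6.2% (slope SD 0 and 0.1) and 8.5% (slope SD 0.2). It is a usable alternative. Its drawback is that total duration is itself ended by ROSC and is not known when a prediction would be made.
- **The same timing occurs elsewhere.** The secondary comparison of PI with ETCO₂ also uses first and last values, and the last value is again timed by the outcome. This is correct. Rewording ΔPI alone leaves that comparison as it is.

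**Conclusion.** The concern holds. The Protocol fixes an outcome-timed interval and names only baseline adjusters, so this is a stated rule and not a detail left to a later document. As defined, the Goal 2 estimate mixes any link between PI trend and ROSC with how long each group was observed, and a reader of the result could not separate the two.

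The bias needs both drift and unequal interval lengths. In the main simulations, false positives run from nominal to 57% with a constant chance of ROSC per cycle and reach 82% when that chance falls. The second, less noisy set goes higher. All of this rests on assumed drift, durations and spread, and the Protocol does not show where this study lies. The definition should be changed before analysis. The primary sensitivity and specificity endpoint and the sample size do not depend on it.

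**What to change.** Replace the outcome-timed ΔPI with text such as:

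> At each cycle from the second onward, ΔPI is the 2-minute mean PI of that cycle minus that of the first monitored cycle. It is related to ROSC in the next cycle in a discrete-time logistic model with cycle number, age, initial rhythm, no-flow time, bystander CPR and sex, and patient-clustered standard errors.

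This reuses the next-cycle outcome the Protocol already sets for PI values. In the null cases above that were run with it, false positives were 5.5–7.1%. ΔPI at a fixed landmark can be a sensitivity analysis.

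**Cost.** One definition is reworded and the analysis is slightly longer, on the same recordings. Patients with ROSC in the first or second monitored cycle give no change value. In the base case 30.4 of 37.0 events remain (a loss of 6.6 / 37.0 = 18%) for 7 coefficients. With shorter efforts 27.5 remain, and with a falling chance of ROSC 25.4. These patients add little under the present rule too. ROSC in cycle 1 has no preceding cycle, and for ROSC in cycle 2 the preceding cycle is the initial one, so ΔPI is 0 if the initial PI is the first two-minute mean. No particular power is claimed for the replacement.

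### The adjusted ΔPI model has about 35 ROSC events for at least six coefficients, so a standard maximum-likelihood fit would on average exaggerate any real effect by about 10–20% on the log-odds scale; a Firth fit is a cheap improvement.

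*Protocol*

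**What the plan says.** Under Statistical Analysis Plan, Primary Endpoint, the protocol defines the trend measure as "the difference (ΔPI) between initial PI and PI values of the cycle preceding ROSC or the last cycle in the absence of ROSC". It will then "examine the association between ΔPI and ROSC through a multivariable logistic regression while adjusting for predetermined baseline confounders such as age, initial rhythm", with no-flow time, bystander CPR and sex completing the named list. No estimation method, interval type or rhythm coding is stated.

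Sample Size Calculations assumes "an expected prevalence of ROSC of 40" per cent, an "expected sensitivity and specificity of 90% for PI to predict ROSC", and "a precision of 10% and a type I error rate of 0.05". From these, "we calculated a required sample size of 87", and "Including a possible dropout of 5% we calculated a final sample size of 92". That calculation concerns sensitivity and specificity only; nothing in it refers to the ΔPI model.

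The Background section names four rhythms and groups them as shockable (two) and non-shockable (two).

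**The concern.** Maximum likelihood is the default meaning of an unqualified multivariable logistic regression. With few events per coefficient its estimates are biased away from zero on the log-odds scale. The sample size was not chosen with this model in mind, and the wording leaves the covariate list open, so the ratio could fall further.

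The ΔPI odds ratio is the only analysis planned for the second of the listed goals, the association between change in perfusion index and ROSC. If a real effect exists, readers would on average be given too large a figure with more sampling error than necessary. A second, conditional problem is the rhythm term. If rhythm enters as four categories, a sparse one may contain only ROSC or only non-ROSC patients, and its coefficient then has no finite maximum-likelihood estimate.

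**Working it through.** **The plan's own figure.** Patients with ROSC needed for sensitivity: 1.96² × 0.9 × 0.1 / 0.1² = 34.57. Dividing by 0.40 gives 86.4, rounded up to 87. The specificity side needs 34.57 / 0.60 = 57.6, rounded up to 58, so sensitivity governs. Dropout: 87 / 0.95 = 91.6, rounded up to 92. Both stated figures reproduce, and this point does not affect them.

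**Events per coefficient.** Expected ROSC events: 87 × 0.40 = 34.8, the smaller outcome group. ΔPI, age, sex, no-flow time and bystander CPR take one coefficient each if the continuous terms are linear, which makes 5. Rhythm adds 1 (shockable or not) or 3 (four rhythms), so the total is 6 to 8.

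- 6 coefficients: 34.8 / 6 = 5.8
- 8 coefficients: 34.8 / 8 = 4.35
- If all 92 were evaluable: 36.8 / 6 = 6.1 and 36.8 / 8 = 4.6

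**Effect on the ΔPI odds ratio.** Simulation with 87 patients, about 40% ROSC and 1,500 data sets per scenario. The protocol gives no covariate effects, rhythm shares or ΔPI effect, so these are assumptions: 25% shockable in the 6-coefficient model, and rhythm shares of 50/25/20/5% in the 8-coefficient model. ORs are per SD of ΔPI, averaged on the log scale; ML is maximum likelihood.

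| True OR | Coefficients | ML OR | ML log-OR bias | Firth OR | SD of log-OR, ML / Firth | ML Wald coverage |
|---|---|---|---|---|---|---|
| 1.0 | 6 | 1.00 | none | 1.00 | 0.284 / 0.254 | 94.6% |
| 1.5 | 6 | 1.58 | +12.3% | 1.50 | 0.298 / 0.264 | 94.9% |
| 1.5 | 8 | 1.61 | +18.2% | 1.52 | 0.316 / 0.271 | 94.3% |
| 2.0 | 6 | 2.18 | +12.2% | 2.00 | 0.325 / 0.284 | 94.9% |
| 2.0 | 8 | 2.22 | +14.8% | 1.99 | 0.339 / 0.286 | 94.9% |
| 3.0 | 6 | 3.47 | +13.3% | 3.00 | 0.398 / 0.337 | 95.1% |
| 3.0 | 8 | 3.73 | +19.8% | 3.08 | 0.418 / 0.335 | 94.9% |

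Other runs gave 2.15 (6 coefficients) and 2.25 (8 coefficients, rarest rhythm 2%) for a true OR of 2.0. Since ln 2.15 / ln 2 = 1.10, the overall range is about +10% to +20%. As a contrast, 350 patients with 6 coefficients gave +3%.

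Relative to sampling error, with 6 coefficients and a true OR of 2.0: bias = 0.778 − 0.693 = 0.085, and 0.085 / 0.325 = 0.26 SD. Over true ORs of 1.5 to 3 with 6 coefficients it runs from about 0.2 to 0.4 SD. With 8 coefficients it reaches about 0.5 SD at a true OR of 3 ((1.316 − 1.099) / 0.418).

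Root mean squared error, same scenario: ML √(0.325² + 0.085²) = 0.336; Firth √(0.284² + 0.002²) = 0.284, about 15% lower. Firth therefore reduces bias and variance together.

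**Rare rhythm category.** If a category has share q and within-category ROSC probability p, the chance that it is empty or has only one outcome among 87 patients is (1 − q + qp)⁸⁷ + (1 − q + q(1 − p))⁸⁷ − (1 − q)⁸⁷. With p = 0.4:

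- q = 10%: 3%
- q = 5%: 0.071 + 0.172 − 0.012 = 23%
- q = 2%: 67%

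With p = 0.7 the three figures are 7%, 30% and 71%. With shockable versus non-shockable coding at 25% shockable, the simulation produced no such case.

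**The case against.** The strongest reply is that the estimator and factor coding are details for a statistical analysis plan, and that a Firth fit is itself a multivariable logistic regression. Part of this stands: maximum likelihood is inferred, not stated, and a separate plan that is not shown may already settle the matter. But the protocol has its own statistical analysis section, which names the model and its covariates. The point concerns how well that model suits about 35 events.

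Second, inference under maximum likelihood is not damaged. This stands. Wald coverage is 94–95%, and rejection at a true OR of 1 was about 5–6%. A reader might infer from the low event count that the analysis would produce spurious associations or that its odds ratio is certain to be inflated. Neither follows: the bias is an average over repeated trials, a fraction of a standard error, and absent when there is no effect.

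Third, a reader might infer that the bias favours the sponsor, because Expected outcomes predicts that upward trends go with ROSC. The bias is symmetric and would equally exaggerate an effect in the opposite direction.

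Fourth, the rhythm problem depends on a four-category coding that the protocol does not specify and on shares it does not give. This stands, so no single failure rate can be attached to the plan. A diverging rhythm coefficient also usually leaves ΔPI estimable.

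Fifth, Firth costs power. With Wald tests it does: detection fell from 78% to 72% at a true OR of 2.0 and from 38% to 31% at 1.5. With penalised profile-likelihood tests most of the loss disappears: 73% against 74% for Wald maximum likelihood at 2.0, and 36% against 38% at 1.5 (a separate run), with coverage of 95.5–96.4%.

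Finally, the model supports the primary endpoint of sensitivity and specificity and does not define it. It carries no threshold or success criterion. This stands and limits the weight of the point.

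**Conclusion.** The point holds as a worthwhile, low-cost improvement, not as an error that invalidates the analysis. The event count and the minimum of six coefficients follow from the protocol's own figures. The average exaggeration of about 10–20% on the log-OR scale applies to true odds ratios of 1.5 to 3 per SD under assumed moderate covariate effects. Stronger effects would be exaggerated more (+21% to +35% at an OR of about 13), but the 90% accuracy figures in the protocol concern PI itself and give no basis for assuming such an effect for ΔPI. What suffers is the size and precision of the reported odds ratio. Non-estimable rhythm categories are possible only under a coding the protocol leaves open.

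**What to change.** In Statistical Analysis Plan, Primary Endpoint, state that the adjusted ΔPI model will be fitted by Firth penalised logistic regression, with penalised profile-likelihood intervals and tests in place of Wald ones. Enter initial rhythm as shockable versus non-shockable (one coefficient), and close the covariate list. Keep the maximum-likelihood fit as a sensitivity analysis.

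This needs a sentence or two of text and standard software, with no extra patients or data. The price is slightly conservative intervals, a slightly smaller reported odds ratio, and a power loss of about 1–4 percentage points. Firth cannot estimate an empty category and does not add information beyond the roughly 35 events, which is why the rhythm coding should be fixed along with it.
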